# 2 LIST OF ABBREVIATIONS

ADR: Adverse Drug Reaction ADE: Antibody-mediated enhancement of infection AE: Adverse Event/Adverse Experience APACHE: Acute Physiological Measurement and Chronic Health Evaluation **CBC: Complete Blood Count** CCP: COVID-19 Convalescent Plasm CDC: United States Centers for Disease Control and Prevention CFR: Code of Federal Regulations CLIA: Clinical Laboratory Improvement Amendment of 1988 COI: Conflict of Interest COVID-19: Coronavirus Disease CRF: Case Report Form **CRP: C-Reactive Protein** DMC: Data Management Center DSMB: Data and Safety Monitoring Board EUA: Emergency Use Authorization FDA: Food and Drug Administration GCP: Good Clinical Practice HBV: Hepatitis B virus HCV: Hepatitis C virus HFNC: High flow nasal cannula HIV: Human immunodeficiency virus HTLV: Human T-cell lymphotropic virus IB: Investigator's Brochure ICF: Informed Consent (Informed Consent Form) ICH: International Conference on Harmonization ICU: Intensive Care Unit IEC: Independent Ethics Committee IND: Investigational New Drug Application **IRB: Institutional Review Board** ISBT: International Society of Blood Transfusion ISM: Independent Safety Monitor IWRS: Interactive Web Response System LOS: Length of Stay MERS: Middle East Respiratory Syndrome mNGS: Metagenomic Next generation sequencing MTN: Mid-turbinate nalal NP: Nasopharvngeal OHRP: Office of Human Research Protections **OP:** Oropharyngeal RT-PCR: Reverse Transcriptase Real-Time Polymerase Chain Reaction PK: Pharmacokinetic **RDV: Remdesivir** SAE: Serious Adverse Event SARS: Severe Acute Respiratory Syndrome SARS-CoV-2: Severe Acute Respiratory Syndrome Coronavirus 2 SOFA: Sequential Organ Failure Assessment TACO: Transfusion-associated Circulatory Overload T. cruzi: Trypanosoma cruzi TRALI: Transfusion-related Acute Lung Injury **UP: Unanticipated Problem** 

# 3 PROTOCOL SUMMARY

Long title: A randomized controlled adaptive study comparing COVID-19 convalescent plasma (CCP) to non-immune plasma to limit coronavirus-associated complications in hospitalized patients.

Sample Size: n=50

**Study Population:** Hospitalized COVID-19 patients aged ≥18 years with respiratory symptoms and hypoxia, who do not currently require mechanical ventilation, enrolled within 3 days of admission to the hospital OR within 14 days of initial onset of symptoms.

Study Duration: May 25, 2020 to April 30, 2021

**Study Design**: This randomized, pragmatically blinded, placebo-controlled, adaptive trial will assess the efficacy and safety of anti-SARS-CoV-2 convalescent plasma in hospitalized patients with acute respiratory symptoms up to 14 days after the onset of initial symptoms.

A total of 50 eligible subjects will be randomized in a 1:1 ratio to receive either convalescent fresh frozen plasma from blood donors who have recovered from COVID-19 containing antibodies to SARS-CoV-2 or control (standard fresh frozen plasma collected prior to 12/1/2019 or with documented negative SARS-CoV-2 antibody). Should additional anti-COVID agents (anti-viral and/or anti-inflammatory) become available for use as standard of care during implementation, the sample size will be recalculated and increased to account for the estimated impact that these agents may have on the reducing the progression to the primary endpoint of severe hypoxemia.

#### **Clinical, Laboratory and Imaging Data**

- 1. Date of symptom onset and history of presenting illness
- 2. Demographics: Age, sex, comorbidities, zip code + 4
- 3. Vital Signs: Temperature, respiratory rate, blood pressure, oxygen saturation, oxygen requirements, APACHE score, SOFA score.
- 4. Laboratory Data:
  - Hematologic Markers: CBC with differential (neutrophil, lymphocyte counts explicitly recorded), PT/PTT, D-dimer
  - Metabolic Markers: Creatinine, liver function tests
  - Inflammatory Markers: CRP, ferritin
  - Arterial blood gas values, if available
  - Measurement of isotype, total antibody, and neutralizing capacity of donor plasma antibodies to SARS-CoV-2
  - Serum or plasma antibody to SARS-CoV-2: Day 1, 5,8,15, 29, 120
  - SARS-CoV-2 PCR from nasopharyngeal swab (NP) or mid-turbinate nasal swab (MTN Day 1,2,5,8,15
- 5. Chest imaging (CT or Chest x-ray): obtained as part of standard care

**Primary Objective:** Evaluate the efficacy of convalescent fresh frozen plasma from blood donors who have recovered from Covid-19 containing antibodies to SARS-CoV-2 versus control (standard fresh frozen plasma) to prevent severe hypoxemia during the 14 days after administration in hospitalized patients with COVID-19 who are within 72 hours of hospital admission OR 14 days of symptom onset.

**Primary Endpoint**: Progression to mechanical ventilation/ECMO for hypoxia/hypercarbia, or death from any cause

Safety and Efficacy of the intervention will be assessed during multiple time points Day 1 (baseline), 2,5,8,15, 29 and once at month 4 (day 120).

OBJECTIVES	ENDPOINTS (OUTCOME MEASURES)
Primary Objective	
Evaluate the efficacy of convalescent fresh frozen plasma from blood donors who have recovered from Covid-19 containing antibodies to SARS-CoV-2 versus control (standard fresh frozen plasma) to prevent mechanical intubation or death within 14 days of CPP administration in hospitalized patients with COVID-19 who are within 3 days of hospital admission or 14 days of symptom onset.	Progression to mechanical ventilation or death within the first 14 days of enrollment. A secondary endpoint will evaluate progression to endpoint within the first 28 days of enrollment.
Key Secondary Objectives	
To evaluate the clinical efficacy of CCP relative to the control arm in adults hospitalized with COVID-19 according to clinical status (8-point ordinal scale) at Day 29	
 
Death;
 
Hospitalized, on invasive mechanical ventilation or ECMO;
 
Hospitalized, on non-invasive ventilation or high flow oxygen devices;
 
Hospitalized, requiring supplemental oxygen;
 
Hospitalized, not requiring supplemental oxygen - requiring ongoing medical care (COVID-19 related or otherwise);
 
Hospitalized, not requiring supplemental oxygen - no longer requires ongoing medical care;
 
Not hospitalized, limitation on activities and/or requiring home oxygen;
 
Not hospitalized, no limitations on activities.
 

OBJECTIVES	ENDPOINTS (OUTCOME MEASURES)
Additional Secondary Objectives	

 
To evaluate the clinical efficacy of different investigational therapeutics as compared to the control arm as assessed by:
 
Clinical Severity Ordinal scale:
 
Time to an improvement of one category and two categories from Day 0 (baseline) using an ordinal scale.
 
Subject clinical status using ordinal scale at Days 2,5,8,15, 29
 
Mean change in the ordinal scale from Day 1 to Days 2,5,8,15, 29
 
	
 
Clinical outcome assessed using ordinal scale daily while hospitalized and on Days 15, 29 and 120
 
Time to clinical recovery (defined as ordinal score 1-3)
 

 
National Early Warning Score (NEWS):
 
Time to discharge or to a NEWS of ≤ 2 and maintained for 24 hours, whichever occurs first.
 
Change from Day 1 to Days 2,5,8,15, 29
 
	
 
NEWS assessed daily while hospitalized
 

 
Oxygenation:
 
Oxygenation use up to Day 120.
 
Incidence and duration of new oxygen use during the study.
 
Oxygen requirement on day 1,2,5,8,15, 29
 
	
 
Days of supplemental oxygen (if applicable) up to Day 29
 
PaO2/FiO2 ratio or SpO2/FiO2
 
O2 requirement at day 120
 

 
Non-invasive ventilation/high flow oxygen:
 
Non-invasive ventilation/high flow oxygen use up to Day 29.
 
Incidence and duration of new non-invasive ventilation or high flow oxygen use during the study.
 
	
 
Days of non-invasive ventilation/high flow oxygen (if applicable) up to Day 29
 


 
Invasive Mechanical Ventilation / extracorporeal membrane oxygenation (ECMO):
 
Ventilator / ECMO use up to Day 29.
 
Incidence and duration of new mechanical ventilation or ECMO use during the study.
 
	
 
Days of invasive mechanical ventilation/ECMO (if applicable) up to Day 29.
 

 
Hospitalization
 
Duration of hospitalization (days).
 
	
 
Days of hospitalization as of Day 29 and day 120
 

Mortality 
 
15-day mortality
 
29-day mortality
 
120-day mortality
 
	
 
Date and cause of death (if applicable)
 

To evaluate the safety of CCP as compared to the control arm as assessed by:	• SAEs

 
Cumulative incidence of SAEs through Day 29.
 
Cumulative incidence of Grade 3 and 4 clinical and/or laboratory AEs through Day 29.
 
Transfusion associated adverse events
 
	
 
Grade 3 and 4 AEs
 
Grade 2 or higher AE's attributed to CCP
 

 
Exploratory Objectives
 
To evaluate the virologic efficacy of CCP
 
	

 
as compared to the control arm as assessed by:
 
Percent of subjects with SARS-CoV-2 detectable in nasal sample at Days 1,5,8,15
 
Quantitative SARS-CoV-2 virus in NP/MTN sample at Days 1,2,5,8,15
 
	
 
Qualitative and quantitative polymerase chain reaction (PCR) for SARS-CoV-2 in NP/MTN swab on Day 1,2,5,8,15 (while hospitalized)
 

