# 4.1.4 **Target population**

This study will enroll hypoxic hospitalized COVID-19 patients, a group that is at elevated risk for poor outcomes and progressive respiratory failure. To date, approximately 30-50% of hospitalized San Francisco COVID-19 patients have required intensive care level treatment, the majority due to respiratory failure[1]. This high progression to ICU level care due to respiratory failure has been seen across the US. This study targets patients who are still early in the course of disease, when CCP may be most effective, the "green zone" described in Figure 2. Once severe respiratory decompensation and ARDS occur and patients have progressed to the "red zone", CCP may be less effective, as was the case with use of CCP in SARS-1 -[8]. The study has been amended to include those on high flow nasal oxygenation, as well as those on nasal cannula. In the ACTT-1 study, 25% of participants on HFNC (ordinal group 6) progressed to mechanical ventilation or death [22] These individuals are at elevated risk of progression to intubation and it is important to understand if CCP can reduce deterioration of respiratory status.

This study will permit enrollment of pregnant women, breastfeeding women and women of childbearing potential. CCP should not pose a pregnancy specific risk, other than the known risks associated with blood product infusions in general. However, for pregnant or breastfeeding women, additional counseling will be provide as to the lack of data for CCP use in COVID-19 infection during pregnancy and lactation and that an adverse event that impacts the participant could also affect an unborn child by affecting maternal health. Pregnant women who chose to enroll will have the pregnancy outcome recorded.

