# 8 point WHO ordinal Scale of clinical status[28]

# **Ordinal Scale for Clinical Improvement**

Patient State	Descriptor	Score
Uninfected	No clinical or virological evidence of infection	0
Ambulatory	No limitation of activities	1
	Limitation of activities	2
Hospitalized Mild disease	Hospitalized, no oxygen therapy	3
	Oxygen by mask or nasal prongs	4
Hospitalized Severe Disease	Non-invasive ventilation or high-flow oxygen	5
	Intubation and mechanical ventilation	6
	Ventilation + additional organ support – pressors, RRT, ECMO	7
Dead	Death	8

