# 6 STATISTICAL PLAN

#### 6.1 Sample Size and Power Considerations

All power calculations were performed using Stata "power" package assuming a two-tailed  $\alpha$ =0.05. The planned sample size for the trial is 50 subjects, randomized in a 1:1 ratio to anti-SARS-CoV-2 convalescent plasma versus control plasma. The primary analysis will compare the combined endpoint of mechanical ventilation or death in the anti-SARS-CoV-2 convalescent plasma and control groups.

We base our sample size projection on the ACTT-1 data [22]They reported the progression within 15 days separately for COVID-19 hospitalized requiring supplemental oxygen and those requiring high flow oxygen or non-invasive ventilation. The proportion progressing were 20% and 34%, respectively in the standard of care group and 8% and 25% in the remdesivir group progression. For our assumption we assume a 32% progression rate on the standard of care (no convalescent plasma) In the absence of treatment with convalescent plasma, we anticipate that between 10 to 30% will experience the primary outcome of mechanical ventilation or death . Using the Fisher exact test: we will reject the null hypothesis under the data scenario in the Table below.

No. Mechanical ventilation/Death (%)	Control arm (%)	Active arm (%)
	5/25 (20%)	0/25 (0%)
	6/25 (24%)	<= 1/25 (4%)
	7/25 (28%)	<= 1/25 (4%)
	8/25 (32%)	<= 1/25 (4%)
	9/25 (36%)	<= 2/25 (8%)
	10/25 (40%)	<= 3/25 (12%)

Rejection Region for the Fisher Exact Test

We will use an 8-point ordinal scale to assess clinical status, based on WHO clinical trial guidance. We assume the same distribution of outcomes for the control arm (i.e., in the absence of treatment with

convalescent plasma) as in ACTT, as tabulated below. Assuming 25 participants are treated with convalescent plasma and 25 participants are untreated, we would have 80% power to detect a difference between treatment arms as follows:

Category	Control arm (%)	Active arm (%)
Death	12%	0
Hospitalized, on invasive mechanical ventilation plus additional organ support (pressors, RRT, ECMO)	0	0
Hospitalized, intubated and mechanical ventilation	20.0%	0
Hospitalized, on non-invasive ventilation or high flow oxygen devices;	12%	8%
Hospitalized, requiring supplemental oxygen fy mask or nasal prong	0	20%
Hospitalized, not requiring supplemental oxygen – requiring ongoing medical care (COVID-19 related or otherwise);	24%	12%
Not hospitalized, limitation on activities	16%	28%

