# 6.2 Statistical Analysis

# 6.2.1 **Primary endpoint**

Our primary hypothesis is that by providing anti-SARS-CoV-2 plasma, the rate of progression to mechanical ventilation or death will be decreased as compared to the rate in in the group receiving control plasma. We will apply a Fisher exact test to compare the combined endpoint of mechanical ventilation/death respiratory failure rates between the two groups occurring by day 15. 29. All analyses

will be conducted with a modified intention-to-treat approach, which excludes randomized subjects who do not initiate an infusion of the study plasma. As secondary analysis, we will also analyze the reduced oxygenation rate, requirement for supplemental oxygen rate, length of hospitalization, time to recovery (ordinal score 1-3) and mechanical ventilation rate, respectively, as well as occurrence of the primary endpoint by day 29 Statistical inference will be based on a two-sided Type 1 error rate of 0.05 and 95% confidence intervals.

Participants who are intubated for reasons other than hypercarbia/hypoxia, such as for a procedure or airway obstruction, will have ventilation settings evaluated to determine if need for ventilation due to hypoxia is meet. This will be determined by >12 hours of requirement for a mandatory mode of ventilation (volume control or pressure control) or Fi02 of > 40%. External adjudication of intubation for non-hypoxic/hypercarbic indication will be conducted.

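### The key secondary objective is status at Day 29, but the plan does not say whether a multi-day GEE effect or a by-day odds ratio is the result, and its ordinal categories and 'recovery' score are not tied to one scale

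*Combined protocol and SAP*

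**What the plan says.** **Objective.** Sections 3 and 5.1 set the key secondary objective as clinical status on an 8-point scale at Day 29. They list eight categories without scores, from worst to best. Invasive ventilation and ECMO share one category. Inpatients without oxygen have two, split by need for care; one of them is "Hospitalized, not requiring supplemental oxygen - no longer requires ongoing medical care".

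**Scored scale.** The only 8-point scale with printed scores is the WHO table in the study procedures (Section 5.4). It runs from 0 to 8, has two ventilation levels, and has one level, score 3, for "Hospitalized, no oxygen therapy".

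**Sample size.** Section 6.1 says "We will use an 8-point ordinal scale to assess clinical status, based on WHO clinical trial guidance". Its table uses the WHO levels 1 to 8, but the no-oxygen inpatient row carries the list's wording, "requiring ongoing medical care (COVID-19 related or otherwise".

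**Analysis.** Section 6.2.2 names the WHO scale and a proportional-odds model, with GEE because status is measured on several days. It lists no model terms. Section 6.2.3, on other secondary endpoints, says that the ordinal scale by day will be summarized by arm, with proportions and with odds ratios and 95% confidence intervals.

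**Recovery.** The objectives tables give "Time to clinical recovery (defined as ordinal score 1-3", and Section 6.2.1 repeats "time to recovery (ordinal score 1-3". Neither place names a scale.

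**The concern.** An objective fixed at Day 29 needs one Day 29 estimate, chosen in advance. The plan has two candidates: a GEE whose treatment effect, if a single odds ratio is fitted, averages over visits, and a by-day odds ratio that is only described as a summary and may or may not be a proportional-odds one. If the effect changes over time these estimate different quantities, and nothing in the text settles which one is reported.

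The categories matter for the same reason. The split by need for care cannot be rebuilt from a WHO score, and whether an inpatient off oxygen counts as recovered depends on which scale the scores 1 to 3 refer to.

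**Working it through.** **1. The two scales side by side.** The list prints no scores; the numbering from best = 1 is mine. The last column is the 6.1 table.

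| State | List | WHO | 6.1 control / active |
|---|---|---|---|
| Uninfected | none | 0 | none |
| Home, no limitation | 1 | 1 | 16% / 32% |
| Home, limitation | 2 | 2 | 16% / 28% |
| Inpatient, no oxygen, care not needed | 3 | 3 | no separate row |
| Inpatient, no oxygen, care needed | 4 | 3 | 24% / 12% |
| Supplemental oxygen | 5 | 4 | 0% / 20% |
| Non-invasive ventilation or high flow | 6 | 5 | 12% / 8% |
| Invasive ventilation | 7 | 6 | 20% / 0% |
| Ventilation with organ support or ECMO | 7 | 7 | 0% / 0% |
| Death | 8 | 8 | 12% / 0% |

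One printed number fits the list's numbering and not WHO. Section 4.1.4 says "In the ACTT-1 study, 25% of participants on HFNC (ordinal group 6) progressed to mechanical ventilation or death", and high flow is 6 on the list but 5 on WHO. That is the cited trial's numbering, but Section 6.1 takes its control distribution from the same trial.

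**2. Recovery on the 6.1 table.**
- WHO 1 to 3: control 24 + 16 + 16 = 56%; active 12 + 28 + 32 = 72%; difference 16 points.
- List 1 to 3: let s be the share of the 24%/12% row no longer needing care (assumed equal in both arms). Control is (32 + 24s)%, active (60 + 12s)%, difference 28 - 12s points. At s = 0, 0.5 and 1 this is 28, 22 and 16.
- The two readings therefore differ by 0 to 12 points.

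**3. The stated 80% power.** Section 6.1 names no test for this figure. Inputs: 25 per arm, two-sided 0.05, the table above.
- A t-test on equally spaced category scores (means 4.04 and 5.56, pooled SD 1.86 to 1.90) gives 79.2% to 80.8%, which reproduces the plan's figure.
- For the planned model, a proportional-odds fit to the table gives log OR 1.255, OR 3.51, 95% CI 1.26 to 9.80. Whitehead's formula has V = N(1 - sum of cubed mean proportions)/12 = 50 x 0.96648/12 = 4.027. Then 1.255 x sqrt(4.027) = 2.519, and 2.519 - 1.960 = 0.559, which is 71.2% power. A likelihood-ratio simulation gave 71.7%. About 62 participants would be needed for 80%.

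**4. Common versus Day 29 odds ratio.** The documents give no time course, so these are illustrations. I used the fitted thresholds, took log OR 1.255 as the full effect, and fitted one common odds ratio to the expected proportions at Days 2, 5, 8, 15 and 29 (independence). Ranges cover fits with and without a visit term, and a control arm worse at Day 1 than at Day 29 by 0, 1 or 2 log odds.

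| Assumed effect (fraction of 1.255 by visit) | Day 29 OR | Common OR |
|---|---|---|
| Constant (1, 1, 1, 1, 1) | 3.5 | 3.2 to 3.5 |
| Builds to Day 8 (0.14, 0.57, 1, 1, 1) | 3.5 | 2.3 to 2.5 |
| Linear to Day 29 (0.04, 0.14, 0.25, 0.5, 1) | 3.5 | 1.5 to 1.6 |
| Fades (1, 1, 1, 0.5, 0) | 1.0 | 2.3 to 2.4 |

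**5. Baseline level.** Section 6.1 shows that oxygen level is prognostic: "The proportion progressing were 20% and 34%, respectively in the standard of care group" (supplemental oxygen and high flow or non-invasive ventilation, respectively). Section 5.3.5 states no stratification factor. If 20%, 30% or 50% of participants are on high flow (assumed, with simple randomization), the chance that the arms differ by 5 or more of 25 is 11%, 16% or 20%.

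**6. Precision of a Day 29 contrast.** Relative to a five-visit mean with equal within-patient correlation r (assumed), the standard error ratio is 1/sqrt((1 + 4r)/5): 1.51, 1.29 and 1.15 at r = 0.3, 0.5 and 0.7.

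**The case against.** A reader might infer that the plan offers nothing but an all-visit GEE and has no Day 29 comparison. The documents do not support that. Section 6.2.3 plans by-day odds ratios with intervals, and Day 29 is one of the days. Nor does 6.2.2 describe a model without a time term; it simply lists no terms. A multi-day model also serves a separate stated objective, status at Days 2, 5, 8, 15 and 29. What stands is narrower: no text says which estimate is the key secondary result, or whether the by-day odds ratio is a proportional-odds one.

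A reader might also infer that recovery cannot be determined. That is too strong. Section 6.2.2 names the WHO scale, the only 8-point scale with scores, and the list must be both numbered and reversed to compete with it. The 11-point scale is scheduled only at Days 15 and 29, so it is an unlikely basis for a time-to-recovery endpoint. WHO is the natural reading, but the definition should say so.

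Finally, an unadjusted randomized comparison is valid. Adjustment for Day 1 score is recommended for precision and against chance imbalance, not because the planned comparison would be biased. The time courses and imbalance inputs are assumptions and do not measure an error in this plan.

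**Conclusion.** The point holds for secondary endpoints only; the primary endpoint is untouched. Two things are on the page. A Day 29 objective is paired with a multi-day model and a separate by-day summary, with no stated choice between them. The objectives' categories conflict with the scale to be analysed at the ventilation levels, at the no-oxygen inpatient level and at score 0.

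The possible size of the first problem is a common odds ratio of about 1.5 to 3.5 when the Day 29 odds ratio is 3.5, or 2.3 to 2.4 when the Day 29 effect has gone. This rests on assumed time courses and on treating the 6.1 table, which names no day, as Day 29. The size of the second is 0 to 12 points in the recovery difference. That is a snapshot of a planning table, not a time-to-event result. Confidence is medium, and the change is worth making because it is cheap.

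**What to change.** - **Scale.** Use the WHO 0-8 scale throughout. Align the category lists in Sections 3 and 5.1 and the row label in 6.1 with it. State in the objectives tables and 6.2.1 that recovery is a WHO score of 3 or lower.
- **Key secondary result.** In 6.2.2, name the Day 29 treatment odds ratio from a proportional-odds model, either single-day or GEE with a treatment-by-visit term and a Day 29 contrast. Adjust for the Day 1 ordinal score, which Table 1 and the Day 1 procedures already collect. Keep the all-visit GEE and the 6.2.3 by-day summaries as supportive.
- **Power.** Restate the 80% in 6.1 for the chosen model, or name the test behind it.
- **Optional.** Section 5.3.1 requires low saturation on room air but not oxygen use, so a participant could be at WHO 3 on Day 1 and count as recovered at time zero. Each would be 1 of 25 (4%) of an arm. Section 4.1.4 describes patients on nasal cannula or high flow, so there would probably be few. Report the number and give time to recovery without them as a sensitivity analysis.

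These are wording changes with no new data. The costs are a standard error about 1.15 to 1.5 times that of a pooled effect (correlation 0.7 to 0.3, assumed), power of about 71% rather than 80% for an unadjusted single-day comparison, and loss of the split by need for care.

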# 5.4 Study procedures

#### Table 1: Schedule of Evaluations

Study period	Screen	Enrollment	Transfusion (within 24 hours of randomization)	Follow up					
Day	Within 3d prior to enrollment	1 (values within 24 hours prior to enrollment)	1	2	5	8	15	29	120
Visit window					+/-	1 day		+/- 7d	+/- 14d
Eligibility									
Informed consent	Х								
Demographic and Medical history	x								
COVID-19 symptom screen	x								
SARS-CoV-2 RT- PCR for eligibility	within 14								
Pregnancy test	days -								
ABO for plasma compatibility	x								
Chest imaging (CXR or CT scan)	х								
Oxygenation Status	х	Х							
		Study I	Drug Administration						
Randomization		Х							
Drug infusion			Х						
Study Procedures									
Vital signs		Х	XXX 		ily days		x 		
Oxygenation status		Х		d	aily 2-8	3 	х	х	Х

Symptom screen	Х	Х	x	x	х	х	х	х	x
Day	Within 3d prior to enrollment	Enrollment (values within 24 hours prior to enrollment)	Plasma transfusion	2	5	8	15	29	120
Visit window				+/-1 day				+/- 5d	+/- 14d
Concomitant medications		x		x	x	x	(only	x COVID t related	reatment 1)
Assessment with 8- point ordinal scale		x		x	х	х	х	x	x
Assessment with WHO 11 point ordinal scale							x	x	
Chest imaging (CXR or CT scan) 					х		х		
Laboratory testing									
CBC (with absolute lymphocyte count)		х		x 	Х 	Х 	X 	X 	х
Renal function, liver function test		х		x 	Х 	Х 	X 		
PT, PTT, D-dimer, hsCRP, ferritin		х		x 	x 	X 	x 	x 	x
SARS-CoV-2 RT- PCR(NP/MTN swab) 		х		x	X 	X 	x 		
Blood for future testing (includes SARS-CoV-2 Ab) 		Х			x 	x 	x 	X 	X 

Vital sign testing, immediately prior to infusion, 10-20 minutes after start of infusion, at completion of infusion and 30-60 minutes after the end of the infusion, ideally bundled with other required clinical care.  If still hospitalized.

 Record most recent preceding chest imaging, if available and conducted per standard of care

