# Day 15 (phone contact if no longer hospitalized or if in person visit is not feasible )

- 1.COVID-19 symptom screen (fevers, cough, shortness of breath)
- 2. Assessment of clinical status (8-point ordinal scale) & WHO 11 point scale[27] (added to facilitate data analysis across data sets)
- 3. New medical conditions, AE evaluation, concomitant medications
- 4.Oxygenation status: current FiO2 or liters of O2, route of oxygen, and oxygen saturation or PaO2 (if available)
- 5. CBC, comprehensive metabolic panel, inflammatory markers (if seen in person)
- 6. Serological testing: anti-SARS CoV-2 antibody levels if hospitalized
- 7. Nasopharyngeal or mid-turbinate nasal swabs with OP swab if possible (if seen in person)
- 8. CXR (or CT with increased oxygen requirement): day 15,(record most recent imaging prior to day 15, conducted per standard of care)
- 9. Stored samples for future studies(3 EDTA, 1 SST) (if seen in person)

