# Day 29: (in person visit if feasible, phone contact if not)

1. COVID-19 symptom screen (fevers, cough, shortness of breath)

2. Assessment of clinical status (8-point ordinal scale) & WHO 11 point scale[27] (added to facilitate data analysis across data sets)

3. Oxygenation status: current FiO2 or liters of O2, route of oxygen, and oxygen saturation or PaO2 (if available)

4. New medical conditions, AE evaluation, concomitant medications (only recorded if treatment given for COVID-19 after day 15)

5. CBC, inflammatory markers (if seen in person)

6. Blood for stored testing, if feasible (3 EDTA, 1 SST)This will include serological testing for SARS CoV-2 antibodies

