#### 7.1.2 Safety measures

- 1. Safety Evaluations will assess for clinical and laboratory indices of reactions to high antibody level anti-SARS-CoV-2 plasma and determine if they are higher, lower or the same as standard plasma
- 2. Clinical evaluations: Vital signs and symptom screen on days 1-8, 15 and symptom screens on days 29, and 120.
- 3. Laboratory evaluations to include chest radiography (chest x-rays and/or chest CT and/or ultrasound)
- Safety laboratory tests (ABO typing, pregnancy testing, CBC, CRP, and comprehensive metabolic panel) will be performed at the local CLIA-certified clinical laboratory on days 1-8 and 15 as specified by above plan.

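### Change in NEWS is an efficacy outcome out to Day 29, but only inpatients are scored and no rule covers death or discharge, so the only possible comparison is among patients selected by their outcome

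*Combined protocol and SAP*

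**What the plan says.** The objectives tables in Sections 3 and 5.1 give NEWS two outcomes. One is "Time to discharge or to a NEWS of ≤ 2 and maintained for 24 hours, whichever occurs first". The other is "Change from Day 1 to Days 2,5,8,15, 29". The only measurement listed for either is "NEWS assessed daily while hospitalized".

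The rest of the document does not supply the missing scores:

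- **Table 1** has no NEWS row. Its Day 15 vital-signs entry carries the footnote "If still hospitalized", and it has no vital-signs entry at Day 29.
- **Section 7.1.2** agrees: "Vital signs and symptom screen on days 1-8, 15 and symptom screens on days 29, and 120".
- **The Day 15 visit list** allows "phone contact if no longer hospitalized or if in person visit is not feasible", and the Day 29 list allows "in person visit if feasible, phone contact if not". Neither list includes vital signs or NEWS.
- **Section 6.2.1** uses a modified intention-to-treat set that leaves out only patients whose infusion was never started. Patients who later die or are discharged stay in it.
- **Section 6.2.3** covers time-to-event, duration, binary and categorical data. It gives no method for a change score.
- **Section 6.2** as a whole never names NEWS and has no rule for scoring death, discharge or a missing value.

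**The concern.** A change from Day 1 needs a score on the later day. A patient who has gone home or died has none under this plan, and nothing assigns one. The ordinal scale has levels for ambulatory and dead patients; NEWS as planned does not.

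Discharge and death are themselves results of treatment. An arm that sends more patients home loses its mildest cases from the NEWS comparison, and an arm with more deaths loses its sickest. The patients left are no longer comparable by randomisation, even though every one of them was randomised. Collecting more inpatient vital signs would not help, because the gap lies in those who have left or died.

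At stake is the reading of one secondary efficacy result. A benefit could appear as no difference, or as a worse NEWS on active treatment.

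**Working it through.** The plan states no effect size, power or sample size for NEWS, so there is no figure of its own to reproduce. The steps below use the ordinal planning table in Section 6.1 at 25 per arm.

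**1. How many patients would have a score**

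| Status | Control | Active |
|---|---|---|
| Dead | 12% = 3 | 0 |
| Ventilated | 20% = 5 | 0 |
| Non-invasive ventilation or high flow | 12% = 3 | 8% = 2 |
| Supplemental oxygen | 0 | 20% = 5 |
| In hospital, no oxygen | 24% = 6 | 12% = 3 |
| Discharged | 16% + 16% = 8 | 28% + 32% = 15 |

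Alive and in hospital:
- control 5 + 3 + 0 + 6 = 14 (56%)
- active 0 + 2 + 5 + 3 = 10 (40%)

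Without a score:
- control 3 deaths + 8 discharges = 11
- active 0 deaths + 15 discharges = 15

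In total 26 of 50 are unscored, and the mix of reasons differs by arm.

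**2. Effect on a rank comparison**

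The six statuses are ranked as in the table, as a stand-in for NEWS. The probability index is the share of control-active pairs in which the active patient is better, with ties counted as half.

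- All patients: 3×25 + 5×25 + 3×(23 + 1) + 6×(15 + 1.5) + 8×7.5 = 75 + 125 + 72 + 99 + 60 = 431; 431/(25×25) = 0.690.
- Inpatients only: 5×10 + 3×(8 + 1) + 6×1.5 = 50 + 27 + 9 = 86; 86/(14×10) = 0.614.
- Leaving out discharges only: (30 + 86)/(17×10) = 0.682.
- Leaving out deaths only: (125 + 72 + 99 + 60)/(22×25) = 356/550 = 0.647.

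**3. Can the sign reverse?**

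Start from the 14 control inpatients (5 ventilated, 3 on non-invasive ventilation or high flow, 6 without oxygen) and change one exit at a time. The NEWS values are assumed. The comparison is of follow-up levels, which carries over to change if Day 1 means are equal in the groups compared.

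| Assumed NEWS (ventilated / non-invasive or high flow / no oxygen) | Control inpatient mean | 3 deaths become ventilated survivors | 6 mildest are discharged |
|---|---|---|---|
| 7 / 6 / 1 | 59/14 = 4.21 | 80/17 = 4.71 | 53/8 = 6.625 |
| 9 / 7 / 2 | 78/14 = 5.57 | 105/17 = 6.18 | 66/8 = 8.25 |
| 12 / 8 / 3 | 102/14 = 7.29 | 138/17 = 8.12 | 84/8 = 10.50 |

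Both changes are real benefits, and in every row the inpatient mean gets worse.

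**The case against.** The strongest reply is that the plan never states an inpatient-only comparison. That is correct: it states no analysis of NEWS change at all. A reader might infer that inpatient-only analysis is the chosen method, but the documents do not say so. It follows only because no other scores would exist and no rule creates them.

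The efficacy question is also partly covered elsewhere. The companion NEWS outcome counts discharge as an event, the ordinal scale has levels for home and death, and mortality and days in hospital are separate outcomes. This stands, and it limits the importance of the point. It does not make the change score interpretable.

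A reader might infer that both exits always pull the comparison toward no effect. That is not supported as a general rule. On the planning table, leaving out discharges alone moves the index only from 0.690 to 0.682, while step 3 shows that either exit can reverse the sign.

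A reader might also turn the index into lost power. Simulated rank-test power on this table falls from about 71% in all patients to about 15% in inpatients, but the contrast should not be used as a measure of bias. With the all-patient distribution kept and only 14 v 10 patients, power is already about 36%, so much of the fall is smaller numbers. The 71% also belongs to the ordinal category, and no test or power is planned for NEWS change.

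**Conclusion.** The point holds for a minor secondary outcome. As written, the plan names a change score that cannot exist for patients who have died or gone home, and the comparison left over is among inpatients selected after randomisation. That conclusion rests on the text alone. At Day 29 even an inpatient's score depends only on the statement that NEWS is assessed daily in hospital, because no vital signs are scheduled. Days 5 and 8 are affected too, once discharges or deaths occur.

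The size is illustrative: about 14 v 10 of 25 per arm scored, and an index of 0.69 in all patients against 0.61 in inpatients. These figures assume that the planning table applies to the day in question, which Section 6.1 does not state, and that ordinal category can stand in for NEWS. They should not be read as describing Day 2 or Day 5. The bias can hide or reverse a benefit, and its direction depends on the scenario. The primary Fisher test and the sample size are not touched.

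**What to change.** Replace the change score in Sections 3 and 5.1, and add a matching paragraph to Section 6.2.3:

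- At Days 2, 5, 8 and 15, rank all modified intention-to-treat patients. Death is worst. Discharged alive and not in hospital that day is best. All others take their observed NEWS.
- Rank readmitted patients by their NEWS. Take a missing inpatient score from the last available inpatient day.
- Compare the arms with a rank-based method adjusted for or stratified by Day 1 NEWS, reporting a probability index with a 95% confidence interval.
- Remove Day 29 as a time point for NEWS change.
- Label any mean change in NEWS points as descriptive among inpatients, shown with the numbers dead and discharged in each arm.

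The cost is wording in the analysis plan. Date of death and days of hospitalization are already collected, and inpatient vital signs are already scheduled on the four days kept. The drawback is that the result is a rank comparison that overlaps with the ordinal scale, not a mean change in NEWS points.
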